A study to evaluate the efficiency of trans-perineal trigger point dry needling combined with manual therapy as a treatment for chronic pelvic pain compared with treatment by manual therapy only: An open-label clinical trial.

> NCT0279502 Version date: 28/08/ 2018

Clinical Research Ethics Committee of the Cork Teaching Hospitals.

Study Protocol

Aim

The presence of myofascial trigger points (MTrPs) or tender points in the pelvic floor muscles (PFM) can attribute to myofascial pelvic pain (MFPP). MFPP is considered to be a cause for chronic pelvic pain (CPP) symptoms including dyspareunia. This study will evaluate the efficiency of including trans-perineal trigger point dry needling (TrDN) with manual therapy to target MTrPs in the PFM compared to manual therapy alone.

The primary objective is to evaluate the number of treatments required within the allocated ten treatment sessions to effect improvement in pain in the treatment groups.

Preface

The aetiology of CPP can originate from urological, gynaecological, gastrointestinal, pelvic neural and pelvic musculoskeletal systems (1,2,3). Non-cyclical CPP does not present exclusively with symptoms of dyspareunia, dyschezia or dysuria. It can present with additional symptoms such as suprapubic and lower abdominal pain, and painful pelvic musculatures (2). The pain can worsen after pelvic floor related activities such as coitus or voiding (4). Furthermore, non-cyclical CPP can also present with worsening of dysmenorrhea symptoms due to hormonal changes, giving a mixed cyclical presentation without the presence of an underlying gynaecological pathology (1).

Due to overlapping symptoms found in cyclical-CPP and non-cyclical CPP and the potential presence of an underlying pathology, a multi-disciplinary approach to diagnosis and management is crucial (1,5). Only 60% of laparoscopic investigations yield a definite diagnosis (6). An inconclusive diagnosis with no evident pathology should suggest myofascial pelvic pain (MFPP) as a probable cause (7). MFPP is caused by the presence of MTrPs in the pelvic muscles, and its presence in PFM can be the primary mediator for non-cyclical CPP (7,8).

Preface to treatments for MFPP

Manual therapy

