In a meta-analysis (23), the study that included TrDN with stretches showed a significant increase in the ROM of the muscles (p=0.043) compared to stretches alone. The treatment duration was three weeks.

An RCT (25) that reviewed stretches combined with TrDN for chronic non-specific neck pain found 58% (n=65) in the combined intervention group required only two treatments from the allocated four to report resolution of symptoms.

A study (26) on temporomandibular dysfunction (TMD) found that the deep TrDN technique for MTrPs (n=36) had a lasting effect for up to six months post-treatment and showed a significant improvement in pain and increased ROM of the jaw after just one treatment for three weeks (p<0.01).

Research Hypotheses

Null hypothesis: The inclusion of trans-perineal TrDN to manual therapy will not influence the number of treatments required to achieve a clinically meaningful reduction in pain within the allocated ten sessions. It will not affect the outcomes for the pain variables and dyspareunia across the categories of treatments.

Research hypothesis: The inclusion of trans-perineal TrDN to manual therapy will influence the number of treatments required to achieve a clinically meaningful reduction in pain within the allocated ten sessions along with a variation in outcomes across the variables evaluated.

Method

This open label non-randomised clinical trial will compare two interventions pre-and posttreatment. This trial will be analysed by intention to treat. The ethical approval was obtained from the Clinical Research Ethics Committee of the Cork Teaching Hospitals in March 2016.

The trial is conducted at the Cork University Maternity Hospital (CUMH) and the Cork Women's Clinic (CWC). CUMH is a large Obstetrics and Gynaecology hospital governed by the Health Service Executive. CWC is a private gynaecology clinic. Female participants will be referred for physiotherapy as deemed appropriate by the inclusion and exclusion criteria (Table 1) given to the gynaecology team at CUMH and CWC.

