The primary objective is to evaluate the number of treatments required within the allocated ten treatments to effect improvement in pain in both groups. Pain resolution will be assessed using the 0-10 Numeric Pain Rating Scale (0-10 NPRS). NPRS will be given at baseline, the fourth, the eighth and the tenth treatment or earlier if resolution of symptoms occurred without the requirement of the allocated ten treatments. The secondary objective is to compare the outcomes between the treatment arms for dyspareunia, bladder and musculoskeletal pain, and some menstrual cycle related pain symptoms with the Female Sexual Function Index questionnaire and an abbreviated version of the International Pelvic Pain Questionnaire (IPPQ). These questionnaires will be completed at pre-treatment and at the final session. The Pain Treatment Satisfaction Scale questionnaire (PTSS) measures the treatment satisfaction in both groups which will be provided only at the final treatment.

Clinical Research Ethics Committee of the Cork Teaching Hospitals.

Table 1: Inclusion and exclusion criteria for recruitment

Inclusion criteria

- Females with non-cyclical CPP including dyspareunia and associated pelvic floor pain-related dysfunctions such as bladder pain, pain with urination or dyschezia.
- They should present with palpable high pelvic floor muscle tone and tenderness on vaginal examination in a clinical setting with a pain score of >4/10.
- They can present with lower abdominal pain, pelvic pain and/or groin pain and pain on sitting.
- Pain worsened with pelvic floor stretching activities like insertion of tampon or intercourse (27).
- Visceral conditions like interstitial cystitis are difficult to exclude at gynaecology review, as they can mimic CPP symptoms (1).
- Smokers are included.
- Nulliparous and parous women included.
- Age 18 to 60 years

Exclusion criteria

- Body mass index greater than 30, as the required needle length is not available.
- Chronic back pain of over 6 month duration and under pain management team.
- Orthopaedic back surgeries with implants.
- Pelvic pathologies like endometriosis, fibroids, cysts and polycystic ovarian syndrome.
- Pregnancy related pelvic girdle pain.
- Pregnant during the trial.
- Pelvic organ carcinomas.
- Undergoing cancer treatment.
- After gynaecology surgery of less than 16 weeks.
- After cardiovascular, gastroenterology, renal or orthopaedic surgery of less than 6 month's postoperative.

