The assessment includes a musculoskeletal assessment for pelvic anatomy and the pelvic and abdominal muscles. The PFM tone will be reviewed with a vaginal and/or rectal assessment (27, 28). The treatment consisted of myofascial TPR of MTrPs in the abdominal, pelvic and pelvic floor muscles and the appropriate stretching for the required muscles. If symptoms included lumbo-pelvic symptoms (27, 29), TPR and stretches for the lumbo-pelvic area will be provided. As a cohort of heterogeneous symptoms is expected to be recruited, an HEP of stretches for the muscles is to be prescribed as per the clinicians' judgement.

Group B: Trans-perineal TrDN with manual therapy

Group B will receive an identical assessment as group A. The treatment consists of the addition of trans-perineal dry needling for the PFM and TrDN for the pelvic and the abdominal muscles. The HEP for group B will be prescribed as per the clinician's judgement. Manual therapy is utilised in pelvic floor areas difficult to access with acupuncture needles.

With pelvic floor hypertonicity, pelvic floor contractions are painful and difficult to initiate and the PFM is slow to return to the normal vaginal resting tone (VRT). Performing a few contractions during vaginal assessment can help assess hypertonicity and tightness in the PFM however, Kegel's based pelvic floor muscle training (PFMT) is contraindicated as they can increase pain and hypertonicity and hence PFMT was not advised (7 p.8). The HEP for both groups are lengthening exercises for the PFM assisted with diaphragmatic breathing. Diaphragmatic breathing is influenced and altered by MFPP. An altered breathing pattern can influence the VRT, where the woman guards and holds her PFM with an apical inspiration instead of using a diaphragmatic inspiration to normalise the VRT. Re-education on the breathing patterns is considered as an important HEP for both groups to help prevent guarding and increasing the VRT. (30 p.333-334, 31,32).

Standardisation of assessment

Standardised assessment for both groups will be as follows

- 1. Subjective assessment
- 2. Gynaecological evaluation of PFM
 - Dermatome and myotome examination
 - Intra-vaginal identification of PFM as per Haslam J et al. (28)
 - Muscle status (28)
- 3. Criterions for MTrPs identification in the pelvic muscles and the PFM (33)
 - The muscle should elicits tenderness on palpation
 - Pain reproduced on palpation of an MTrP in the muscle

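### The title, aim and hypotheses name trans-perineal dry needling as the tested addition, but Group B also has pelvic and abdominal muscles needled, so a difference between groups cannot be credited to the trans-perineal part

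*Combined protocol and SAP*

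**What the plan says.** Four statements name the trans-perineal technique as the thing tested.

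- **Title:** "efficiency of trans-perineal trigger point dry needling combined with manual therapy as a treatment for chronic pelvic pain", compared with manual therapy only.
- **Aim:** "This study will evaluate the efficiency of including trans-perineal trigger point dry needling (TrDN) with manual therapy to target MTrPs in the PFM".
- **Null hypothesis:** "The inclusion of trans-perineal TrDN to manual therapy will not influence the number of treatments required".
- **Research hypothesis:** "The inclusion of trans-perineal TrDN to manual therapy will influence the number of treatments required", continuing "along with a variation in outcomes across the variables evaluated".

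The description of the arms is wider. Under Interventions, Group B reads: "The treatment consists of the addition of trans-perineal dry needling for the PFM and TrDN for the pelvic and the abdominal muscles". Table 3.2 repeats this, listing needling, manual release and distension for the PFM and for the pelvic and abdominal muscles, according to presentation. It also lets needling begin in piriformis, rectus abdominis, gluteal and adductor muscles when a woman is particularly nervous. Group A (Interventions and Table 3.1) receives manual release and stretching of the same regions and no needling.

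The objectives are framed by group. The primary objective in Method concerns the "number of treatments required within the allocated ten treatments to effect improvement in pain in both groups", and its other statement, under Aim, does not name the trans-perineal route either. The secondary objective is also set by arm: "The secondary objective is to compare the outcomes between the treatment arms for dyspareunia, bladder and musculoskeletal pain".

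**The concern.** Anyone who writes the conclusion from the hypotheses will say that trans-perineal needling did, or did not, change the number of sessions needed. The arms differ by all the needling, so the design supports no such statement about one part of it.

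The other needling cannot be assumed inert. The plan's own literature review cites evidence that TrDN works for myofascial pain at other body sites, and this is part of its rationale. The research hypothesis extends the claim to every variable evaluated. Musculoskeletal pain is among them, and needling of pelvic and abdominal muscles could plausibly affect it.

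The protocol calls itself the first study of TrDN for the PFM, so its wording may be relied on. A clinic that adopted only trans-perineal needling on the strength of that wording would be using something this trial did not test alone.

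**Working it through.** **1. The plan's own figure.** The Statistical analysis section gives effect size 0.634, SD 1, α 0.05, 80% power and 80 women in total. Assuming a two-sided test and equal groups:

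n per group = 2 × (1.960 + 0.842)² / 0.634² = 15.70 / 0.402 = 39.05, rounded up to 40, so 80 in total.

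The figure reproduces. Power at 40 per group is 80.9% by the normal approximation and 79.96% by the t-test. The calculation is for Group B against Group A as treated, and nothing below alters it.

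**2. What each arm receives.**

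| Component | Group A | Group B |
|---|---|---|
| Manual therapy: PFM, pelvic, abdominal | yes | yes |
| Trans-perineal needling of the PFM | no | yes |
| Needling of pelvic and abdominal muscles | no | per presentation |
| Therapist at CUMH | three physiotherapists, including the researcher | researcher only |
| Therapist at Cork Women's Clinic | researcher | researcher |

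The therapist rows come from Recruitment and allocation.

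**3. What the contrast contains.** Assume for simplicity that effects add. Let P be the effect of trans-perineal needling, q the share of Group B women needled elsewhere, e the effect of that needling in those women, and T the therapist contribution arising at CUMH. The difference between groups is then

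D = P + q × e + T.

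The trial estimates D. The documents give no value for q, e or T, and they plan no analysis by needling site. One equation does not determine P. If q × e and T were both zero, P would equal D. If together they equalled D, P would be zero. The documents exclude neither, so I put no figure on the split.

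**4. Is the other needling marginal?** The documents do not say. Table 2 lists at least one muscle outside the PFM for all four pain patterns, and none of the PFM for posterior pelvic pain. That table guides assessment and does not count needling. On the other side, Table 1 requires PFM tone and tenderness in every woman, so PFM needling is relevant to all of Group B. Neither fact separates the two effects.

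**5. Where the wording sits.** Places naming trans-perineal TrDN as the addition: title, aim, null hypothesis and research hypothesis, which is 4. Statements of the primary objective naming it: 0 of 2.

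**6. Could needling sites still be recorded prospectively?** Recruitment ran to November 2017 and this version is dated 28 August 2018. Taking 30 November as the last recruitment date, the gap is 271 days, or 271 / 7 = 38.7 weeks. Ten sessions two weeks apart span 9 × 2 = 18 weeks, or 9 × 3 = 27 weeks if every session slips by a week. Treatment would outlast the version date only if the wait for a first session exceeded 38.7 − 18 = 20.7 weeks (38.7 − 27 = 11.7 weeks with every session slipped). Most treatment was probably complete, so only existing notes could supply this information.

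**The case against.** The best defence is that the phrase is a label. The Group B heading under Interventions uses it and sets out the wider needling directly beneath, and Table 3.2 repeats the content. The null hypothesis goes on to speak of outcomes across categories of treatment, the objectives compare groups, and the General Linear Model asks whether the groups differ. No planned test isolates the route, and testing a disclosed package is a legitimate pragmatic choice. The harm also depends on a conclusion not yet written.

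Most of this stands, and it is why the point is modest. It does not rescue the aim, which directs the needling at trigger points in the PFM and so reads as a description of the technique. Nor does disclosure in the methods correct a hypothesis that names one component.

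A reader might infer three stronger things, none of which the documents support.

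- **That needling replaces manual therapy in Group B**, because manual therapy is said to be used in pelvic floor areas that needles do not easily reach. The same section calls the needling an addition, Table 3.2 lists release and distension for the same regions, and introductory PFM needling is followed by compression and stretching.
- **That the trial cleanly measures the whole TrDN regimen.** At CUMH the therapist also differs between groups.
- **That the analysis or sample size is invalid.** Both address the difference between groups, and the figure of 80 reproduces.

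**Conclusion.** The point holds as one of attribution in wording. The trial compares a TrDN regimen plus manual therapy with manual therapy alone, mixed with a therapist difference at CUMH. It cannot say how much of any difference belongs to the trans-perineal component.

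The size of any misattribution is unknown. If few Group B women are needled outside the PFM it may be small, but the documents neither give that number nor plan to report it. The conclusion rests on Group B being treated as Interventions and Table 3.2 describe, and on Group A receiving no needling. It needs no assumption about how effective either kind of needling is.

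The correction is worth making before results are reported, because it limits what the trial may claim.

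**What to change.** As a dated clarification, reword or qualify the title, aim, both hypotheses and the reported conclusion along these lines: a TrDN regimen (trans-perineal for the PFM plus pelvic and abdominal muscles per presentation) added to manual therapy, versus manual therapy alone. State that Group B's content has not changed. Do not credit the trans-perineal route specifically. Note that at CUMH the researcher alone treated Group B while three physiotherapists shared Group A.

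If existing treatment notes allow, report descriptively how many Group B women had needling outside the PFM. No new session recording is proposed.

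The cost is wording in four places plus the conclusion, and an optional review of about 80 / 2 = 40 sets of notes, assuming equal groups. The notes may not show the needling site, and the count would not separate the effects. The downside for the sponsor is a narrower claim about the trans-perineal technique.

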- Neurological conditions such as stroke, epilepsy, Parkinson's disease etc.
- Fibromyalgia and chronic fatigue syndrome.
- Undergoing any treatment such as Botox or analgesic injections which can interfere with physiotherapy outcomes.

Exclusion criteria for dry needling

- Extreme needle phobia, rheumatoid arthritis, prolonged corticosteroid treatment, warfarin treatment, heart implants and blood clotting disorders.
- Participant should have no significant learning disability and should be able to understand the procedure to consent for a vaginal examination and for treatment.
- Participant should not require a chaperone during treatment in order to avoid administrative issues.

Clinical Research Ethics Committee of the Cork Teaching Hospitals.

Recruitment and allocation

Women will be invited for the trial with a letter of invitation. On confirmation of interest in the trial, their medical record numbers and names will be documented onto an excel sheet with the month of referral. In order to accommodate for the CUMH physiotherapy waiting list and to allow for the clinical workings at CUMH, an excel sheet with six names will be emailed to the central appointments office at CUMH. Two CUMH secretaries unrelated to the trial will randomly allocate the names into two opaque envelopes marked as group A and group B.

The staff will allocate appointments for group A among three Chartered Physiotherapists in Women's Health and Continence involved in the trial, including the researcher. The participating physiotherapists will have no input in the allocation process and they all have clinical experience of over 15 years.

Group B will be treated only by the researcher who has a clinical experience of eight years using trans-perineal TrDN. An identical procedure will be piloted at the CWC. The researcher will provide the treatment for both groups at the CWC. The participant's file will be marked as Group A or B to inform about allocation. The recruitment process will ran from April 2016 to November 2017.

Withdrawal from participation

An individual can decline participation in the trial at any stage of the trial. If a participant reports needle phobia after group allocation, she will be transferred to group A. If a participant refuses dry needling treatment after starting the treatment in group B, she will be removed from the trial but care will continue.

Interventions

Group A: Manual therapy

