 Group A: 1st treatment – Trial checklist to be completed by the physiotherapist. Consent forms to be filled by the participants. Complete three baseline questionnaires (NPRS, FSFI, IPPQ). Subjective and objective assessment along with education of muscle involvement and treatment entailed. Education on good bladder, bowel and dietary habits if indicated. Signing of consent forms for treatment and the trial. Assess and treat with TPR and distention for the PFM, pelvic and abdominal muscles as per presentation. 4th treatment – complete NPRS 8th treatment or when ceasing treatments due to positive outcomes – to complete four final questionnaires (NPRS, FSFI, IPPQ, PTSS). 10th treatments – if no resolution is achieved, 	Initial assessment of posture, spine and the PFM. Treatment is for 30-45 minutes on consent for treatment. Assess and treat with manual therapy for the PFM, pelvic and abdominal muscles if indicated. Frequency – The treatment is scheduled for every two weeks unless the participant has her menstrual cycle or due to personal issues. The appointment was then rescheduled for the week after. The HEP are stretches for the pelvic musculature as per presentation of CPP pain patterns. The patient is advised the application of cryotherapy for 15 minutes if she was sore after treatment.
complete the final questionnaires and discharge from the trial but care continues.	

Table 3.1: Procedure, treatment and frequency for group A

Clinical Research Ethics Committee of the Cork Teaching Hospitals.

Procedure	Treatment and Frequency
Group B:	
 1st treatment – Trial check list to be completed by the physiotherapist. Consent forms to be filled by the participants. Complete three baseline questionnaires (NPRS, FSFI, IPPQ). Subjective and objective assessment along with education of pelvic muscle involvement and treatment entailed. Education on good bladder, bowel and dietary habits if indicated. Signing of consent forms for treatment, TrDN 	Initial assessment of posture, spine and PFM. Treatment is for 30-45 on consent for treatment. Only introduce TrDN if the participant is happy to start treatment. 2nd treatment - To perform superficial TrDN technique for the PFM as an introduction to the deep needling technique if the patient is apprehensive about TrDN followed by compression and stretching of the PFM. If the participant is particularly nervous, start with needling muscles

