All questionnaires will be filled by the participants prior to their session at CUMH, CWC or at their homes. The data will be stored in secure locked storage at the Physiotherapy department at CUMH. The data collection will be undertaken by the researcher and a physiotherapist unrelated to the trial. On completion of the trial, the data will analysed for correct input by two doctors and one physiotherapist at CUMH who will be appointed as the data monitoring committee. An interim analysis will not be conducted for this trial.

Trial Duration:

The trial aims to run for two years.

References

- 4. Butrick CW. Pelvic Floor Hypertonic Disorders: Identification and Management. *Obstetrics and Gynecology Clinics of North America*. 2009; 36: p. 707–22.
- 8. Faubion SS, Shuster LT, Bharucha AE. Recognition and management of nonrelaxing

pelvic floor dysfunction. Mayo Clinic Proceedings. Elsevier Inc. 2012; 87(2):187-93.

- Weiss JM. Pelvic floor myofascial trigger points: manual therapy for interstitial cystitis and the urgency-frequency syndrome. *The Journal of Urology*. 2001; 166(6):2226–31. Available from: http://www.ncbi.nlm.nih.gov/pubmed/11696740

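### Trial consent and the baseline questionnaires come after the group draw, so knowledge of the arm could influence baseline pain, and women who decline at that visit have already been allocated

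*Combined protocol and SAP*

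**What the plan says.** All references are to the combined protocol and SAP.

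- **Who is drawn** (Recruitment and allocation). "On confirmation of interest in the trial, their medical record numbers and names will be documented onto an excel sheet with the month of referral". This step follows an invitation letter, and no trial consent is recorded at it.
- **The draw** (same section). "Two CUMH secretaries unrelated to the trial will randomly allocate the names into two opaque envelopes marked as group A and group B". Appointments are then made by group, and the participant's "file will be marked as Group A or B to inform about allocation".
- **First treatment** (Tables 3.1 and 3.2, both groups). After the trial checklist comes "Consent forms to be filled by the participants. Complete three baseline questionnaires (NPRS, FSFI, IPPQ"). Assessment and education follow, then a second consent entry. In group A this covers treatment and the trial. In group B it reads "Signing of consent forms for treatment, TrDN" and trial.
- **Place of completion** (Data monitoring). "All questionnaires will be filled by the participants prior to their session at CUMH, CWC or at their homes".
- **Use of baseline** (Statistical analysis and power calculation). The pre-treatment score is the covariate when the groups are compared on mean endpoint pain. Improvement is judged as a 30% or 50% decrease from baseline.
- **Analysis set** (Method). "This trial will be analysed by intention to treat". No rule covers a woman who is drawn and then declines trial consent.

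**The concern.** A baseline score is safe as a covariate, and as the denominator of a percentage change, when it is fixed before anyone can know the arm. Here it is recorded after allocation, in an open-label trial, with no step that keeps the group hidden until the forms are complete. If women in one arm scored their pain higher or lower because they knew or guessed their treatment, both the adjusted endpoint comparison and the responder status would move with no change in the true outcome.

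The second issue is who remains. A woman who declines trial consent at the first visit has already been allocated. Only group B is asked to accept needling, so refusal could be more frequent there. The groups as analysed could then differ from the groups as drawn, and an intention-to-treat set based on the draw would have gaps.

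**Working it through.** **Step 1. Order of events.**

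| Order | Event | Where stated |
|---|---|---|
| 1 | Interest confirmed, name listed | Recruitment and allocation |
| 2 | Names drawn into A or B | Recruitment and allocation |
| 3 | Appointments made by group, file marked | Recruitment and allocation |
| 4 | Questionnaires completed before the session, at the clinic or at home | Data monitoring |
| 5 | Trial consent and baseline NPRS, FSFI and IPPQ listed at the first treatment | Tables 3.1 and 3.2 |

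The session in rows 4 and 5 is the one booked in row 3. Both readings of when the forms are filled in therefore fall after the draw. Nothing describes consent or baseline measurement before row 2.

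**Step 2. The plan's own figure.** Inputs from Statistical analysis and power calculation: effect size 0.634, SD 1, α = 0.05, power 80%. I assume a two-sided test and 1:1 allocation, neither of which is stated.

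n per arm = 2 × (1.960 + 0.842)² × 1² / 0.634² = 15.70 / 0.402 = 39.1, rounded up to 40, so 80 in total. This matches the plan (a one-sided test would give 62). The planned effect is thus a difference of 0.634 SD, and any bias should be compared with it in SD units. Taking consent and baseline earlier leaves this number unchanged.

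**Step 3. Effect of a shifted baseline on the adjusted comparison.** Assumptions, none from the documents: recorded baseline in one arm moves by δ, true pain and endpoint scores do not, and SDs are equal so that the covariate slope equals the baseline-endpoint correlation ρ.

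- Bias = ρ × δ. A baseline recorded too high makes that arm's adjusted result look better. One recorded too low does the reverse.
- Standard error with 40 per arm = √(1 − ρ²) × √(2/40).
- False-positive rate = P(|Z + bias/SE| > 1.96).

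Worked case, δ = 0.25 and ρ = 0.5: bias = 0.125; SE = 0.866 × 0.2236 = 0.194; ratio = 0.65; false-positive rate = 9.9%.

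| δ (SD) | ρ | Bias (SD) | Share of 0.634 | False-positive rate |
|---|---|---|---|---|
| 0.1 | 0.3 | 0.03 | 5% | 5.2% |
| 0.1 | 0.7 | 0.07 | 11% | 7.2% |
| 0.25 | 0.5 | 0.125 | 20% | 9.9% |
| 0.5 | 0.3 | 0.15 | 24% | 10.8% |
| 0.5 | 0.7 | 0.35 | 55% | 59.2% |

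**Step 4. Effect on the responder reference.** A 30% decrease means endpoint ≤ 0.7 × baseline, and a 50% decrease means endpoint ≤ 0.5 × baseline. A shift of δ in recorded baseline moves these thresholds by 0.7δ and 0.5δ in the same direction.

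**Step 5. How many could be lost after the draw.** The plan invites 124 and expects 70% to take part: 124 × 0.70 = 86.8, leaving 124 × 0.30 = 37.2. It does not say whether that 30% falls before or after the draw. The number lost after allocation could therefore be anything from 0 to about 37, and no estimate by arm is possible.

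**The case against.** A reader might infer that baseline scores are in fact distorted by allocation. The documents do not support that. The marked file informs staff, and nothing says that a woman has been told her group when she scores. The invitation letter and consent forms are not in the text available, so what they tell her is unknown. In Table 3.2 the entry naming the needling consent comes after the questionnaires. The earlier entry does not say which forms it means, so exposure before scoring is possible but not shown. This objection stands: what is shown is that the measurement follows allocation.

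A reader might also infer that women who refuse needling are lost without data. That is too broad. Under Withdrawal from participation, a woman reporting needle phobia after allocation moves to group A, and one who refuses after starting in group B is removed, by which time baseline should exist. The point applies only to women who decline trial consent itself. Even that is inferred from the sequence, and some of them may have filled in forms that cannot be used without consent.

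Nor does it follow that every name drawn should enter the intention-to-treat analysis. Women with neither consent nor data can be counted but not analysed.

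Finally, the change may come too late for this cohort: recruitment is given as April 2016 to November 2017, and the version date is 28/08/2018. That limits the remedy for these women, although the order of events remains a weakness of the plan.

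**Conclusion.** The point holds as a cheap improvement. The documents clearly place trial consent and all three baseline questionnaires after the draw, with no safeguard that hides the group until baseline is complete. The score exposed to this is both the model covariate and the reference for the percentage decrease.

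Whether any distortion occurred, and in which direction, cannot be derived from the documents. The range of 0.03 to 0.35 SD, or 5% to 55% of the planned 0.634, rests wholly on the assumed shift and correlation. Its lower end is negligible. Loss of allocated women at the consent step, possibly more in group B, is likewise possible but not quantified. Confidence in the sequence is high; confidence that it had a material effect is limited.

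**What to change.** **Before the draw.** Take trial consent and the baseline NPRS, FSFI and IPPQ when interest is confirmed, before names go to the central appointments office. Draw only women who have consented and completed the baseline. Consent for the procedures stays at the visit. Home completion is already allowed, so the forms could go out with the invitation letter.

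**For women already recruited.** Report by arm how many were drawn and how many declined after the draw. Analyse all consenting women in the group to which they were drawn. State as a limitation that baseline was taken after allocation.

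**Cost.** A short amendment, some postage, and a longer gap between baseline and first treatment because of the waiting list. The retrospective part needs only the allocation lists and the marked files. The sample size stays at 80.
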